9.2 Sample size justification

Approximately 50 subjects will be enrolled. The primary endpoint analysis will consist of a log-rank test of the difference in treatment groups in the time to viral clearance. Based on a recent publication:

(https://www.sciencedirect.com/science/article/pii/S2095809920300631?via%3Dihub)

it is assumed that the median time to clearance for favipiravir would be approximately 4 days, and the median time for SOC would likely be approximately 11 days; this latter estimate may in fact be conservative since SOC is not as likely to reduce viral load as well as the control in the above referenced study. Using two-sided alpha of 0.10 and power of 90% (appropriate for a trial to be used as the justification for a confirmatory, fully-powered blinded and randomized Phase 3 study), and a fixed per-subject observation period of 15 days, an approximate sample size of 25 subjects per arm (total size of 50) would be required.

9.3 Demographic and Baseline Characteristics

Summary statistics will be provided per treatment group for demographic (e.g., age, height, weight, body mass index [BMI], race, gender) and other initial subject characteristics (e.g., medical history, concomitant diseases) will be provided per treatment group and for the total group. The ITT population will be used for the summaries.

9.4 Analysis Populations

The following analysis populations will be defined for the study:

• Intent-to-treat (ITT) population – All subjects randomized to treatment. Subjects in the ITT population will be analyzed based on the treatment to which they were randomized, irrespective of what treatment they actually received. This population was selected for the analysis of the primary and secondary endpoints in order to maintain the benefits of

randomization and avoid the potential bias associated with the non-random loss of the participant.

- Safety population All ITT subjects who received either favipiravir + SOC, or SOC alone. Subjects in the safety population will be analyzed based on the actual treatment they received, irrespective of the treatment to which they were randomized. It is anticipated that the safety population will be the same as the ITT population.
- Modified intent-to-treat (MITT) All subjects of the safety population that have an assessment of viral shedding after randomization and are confirmed COVID-19 positive. Subjects in the MITT population will be analyzed based on the treatment to which they were randomized, irrespective of what treatment they actually received.
- Per protocol (PP) population All MITT subjects who adhere to relevant study procedures and have an outcome assessment. Further specific details defining the analyses to be performed on this population will be described in the SAP.
- PK population (PK) All subjects in the safety population that have at least one result that can be used in the PK summaries.

9.5 Stratification, Subgroup Analysis and Pooled Analysis

The stratification factors used in randomization, critical v. severe v. mild/moderate disease as defined above based on supplemental oxygen requirements, SpO2 status etc., will be accounted for in the efficacy analyses. The stratification factor may be deleted from the statistical model if the interaction is not significant at the 0.10 level. Efficacy data will be pooled across study sites for analysis, after visual inspection of summary results reveals similarity across study sites. Efficacy results may also be summarized within each randomization stratum for exploratory purposes.

9.6 Efficacy Endpoint Analysis

The primary endpoint of time to viral clearance will be analyzed with the log-rank test for treatment difference and summarized using the Kaplan-Meier methodology as noted above. Viral load results from day of discharge as available will also be included in the analysis of viral clearance.

The key secondary endpoint of status of clinical recovery as measured by the study-specific 6-point ordinal scale at Day 15 will be analyzed using ordinal categorical data methods, since it is unlikely that linear differences exist between the elements of the scale (for example, a 1-point difference in magnitude may not apply to each increment on the scale). As an exploratory analysis, sequential binary analysis will be performed, based on successive classification of a subject into categories of less than or greater/equal to each ordinal item on the scale. Longitudinal analysis of the 6-point scale over time on study will also be performed to investigate temporal patterns of improvement.

Time to event endpoints will be analyzed using similar methods as used for the primary endpoint; these will include time to: clinical recovery; defervescence; cough mild or absent; dyspnea mild or absent; SARS-CoV-2 RT-PCR negative in upper respiratory tract.

Categorical endpoints will be analyzed using categorical data analysis methods; continuous data will be analyzed using analysis of variance with treatment and strata as factors.

Missing efficacy data in a trial of hospitalized patients is generally unlikely, and great care will be taken at each study site to ensure that all outcome assessments are obtained as planned in this protocol. However, as treatment of COVID-19 subjects evolves, it is clear some subjects will be discharged from the hospital prior to Day 15. Subjects are asked to return for follow up visits on Days 29, 45 and 60. This requirement is presenting challenges for subjects and in order to ensure that in cases where the subject does not return for their follow up visits, an additional swabbing has been added on the day of hospital discharge (See Section 7.7). Should missing data occur for the primary endpoint, time to viral clearance, such patients will be included in the log-rank analysis as censored observations. Missing clinical outcome data will be evaluated using a variety of methods, including multiple imputation, worst-value assignment, and other methods, to be completely outlined in the statistical analysis plan.

9.7 Safety Analysis

The original exact terms in the electronic data capture (EDC) system used by Investigators to identify AEs other than symptoms of COVID-19 will be fully described and coded according to the Medical Dictionary for Regulatory Activities (MedDRA). Treatment-emergent AEs will be defined as those occurring coincident with start of treatment and through Day 60. TEAEs will be summarized overall and by treatment group and by MedDRA body organ system and preferred term, severity, relatedness, and seriousness.

An overall summary of TEAEs will be presented by treatment, with subject counts and percentages of subjects with the event. This summary will include subjects with any TEAE, any treatment-related TEAE, any serious TEAE, any treatment-related serious TEAE, TEAEs leading to study infusion discontinuation, treatment-related TEAEs leading to study infusion discontinuation, TEAEs leading to death, and treatment-related TEAEs leading to death. The difference in proportions between treatment groups in each of these categories will be calculated.

Summaries of changes over time in laboratory parameters, as well as counts and percentages of laboratory parameters that are Low, Normal, and High compared to the reference ranges will be presented by treatment at each visit and time point. Shift tables will be presented for laboratory parameters with defined severity grades.

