	12. Is on another antiviral or is participating in a clinical trial for the treatment of COVID-19.							
	13. Subject is on ventilator at the time of study entry.							
	14. Is deemed by the Investigator to be ineligible for any reason.							
Treatment Regimen for Favipiravir (Standard dose)	 Favipiravir tablets will be administered orally. If necessary, a slurry may be administered by nasogastric tube. The regimen begins with loading doses of 1800 mg BID on Day 1 (the first 24 hours of treatment at t =0 and t = 12 hours) then maintenance dosing of 1000 mg BID from Day 2 (beginning 24 hours after the start of therapy). Patients with Child-Pugh liver impairment of grade A will have their maintenance dose decreased to 800 mg BID. The total duration of treatment is expected to be 14 days. The dose regimen may be altered, after consultation between the treating physician and the Sponsor, depending on the clinical condition of the patient. 							
Duration of Study Participation	Subjects will participate in the study for up to 60 days: 14 days treatment (or as discussed with the Sponsor) and 46 days follow up.							
Statistical Methods	This study is intended to be exploratory. Based upon available data, two-arm study of approximately 50 total subjects will be sufficient provide reasonable assurance that the endpoints chosen for confirmatory trial will elucidate treatment differences between favipiravir and a control. Statistical significance testing will be used to assess the relative strength of evidence of the primary and secondary endpoints.							
	Randomization will be stratified by:Site							
	• Severity of illness at enrollment:							

o Critical disease:

- Requires supplemental oxygen delivered by non-rebreather mask or high-flow cannula, OR
- Use of invasive or non-invasive ventilation, OR
- Requiring treatment in an intensive care unit, use of vasopressors, extracorporeal life support.
- Severe disease:
 - Evidence of pneumonia on chest x-ray or CT scan, or chest auscultation (rales, crackles), OR
 - SpO2 ≤ 93% on room air OR PaO2/FiO2 < 300 mmHg, OR
 - Requires supplemental oxygen by nasal canula, simple face mask, or other similar oxygen delivery device.
- Mild-moderate disease: SpO2 > 94% and respiratory rate < 24 breaths/min without supplemental oxygen
- There is no planned interim analysis.

Individual Stopping Rule

A subject should be removed from favipiravir treatment if one of the following criteria is met:

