3 DESIGN

This is an open label, randomized, controlled, multicenter Phase 2 study of favipiravir in hospitalized subjects with COVID-19. Subjects will be randomized within their study site and stratified by the severity of their disease to receive either favipiravir + standard of care (SOC) or SOC alone (See Section 9.5 for details).

SOC will be site-specific and based on what each site is currently using for COVID-19 patients.

The dose regimen will be 1800 mg favipiravir BID plus SOC or SOC alone on Day 1 followed by 1000 mg BID favipiravir (800 mg BID for subjects with Child-Pugh A liver impairment) plus SOC or SOC for the next 13 days.

The study will have 14 days of treatment and 46 days of follow-up.

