8.4.3 Evaluating and Reporting of Adverse Events

All AEs (i.e. a new event or an exacerbation of a pre-existing condition) that occur after dosing with favipiravir and after completion of baseline assessments in the SOC alone arm, must be recorded as an AE or SAE (if applicable), on the Adverse Event eCRF and SAE form, as applicable. The Investigator must follow all AEs until the AE resolves, or until the Investigator and/or the Medical Monitor determine the event is chronic or clinically stable. If an AE remains unresolved at the conclusion of the study, the Investigator and Medical Monitor will make a clinical assessment to determine whether continued follow-up of the AE is warranted. All subjects who have received at least one exposure to study therapy will be evaluated for safety of study treatment.

The Investigator should attempt to establish a diagnosis of the event based on signs, symptoms and/or other clinical information. In such cases, the diagnosis should be documented as the AE and not the individual signs/symptoms.

All AEs must be promptly documented on the Adverse Event eCRF and assessed by the Investigator. Details of the event must include the dates of onset and resolution, severity, relationship to study drug, seriousness, and whether the event caused the subject to withdraw from the study, outcome and timing with regard to administration of the study drug.

Severity: Severity should be graded and recorded as follows:

- Mild: Awareness of event but easily tolerated
- Moderate: Discomfort enough to cause interference with usual activity
- Severe: Inability to carry out usual activity, incapacitating, requires medical intervention

Relationship: The relationship of the Adverse Event to the study drug will be determined by the Principal Investigator, and assessed using the following definitions:

• **Related:** There is a distinct temporal relationship between the event onset and administration of the study drug. There is a known reaction to agent or chemical group or

predicted by known pharmacology. The event cannot be explained by subject's clinical state or other factors.

• Unrelated: Evidence exists that the AE has an etiology other than the study drug (e.g., pre-existing condition, underlying disease, intercurrent illness, or concomitant medication).

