#### 4.5.2. Adverse Events

All AEs will be coded using the MedDRA v23.0 coding system and displayed in tables and data listings using system organ class and preferred term. Missing and partial dates will be handled as described in [Section 3.10.2](#).

Treatment-emergent AEs (TEAEs) will be defined as those occurring coincident with start of treatment through Day 60.

In the favipiravir + SOC arm: Adverse event solicitation and recording will begin immediately following the first dose of favipiravir and will include only on-treatment (treatment-emergent) events. Any changes to a subject's health that occur between the signing of the informed consent and dosing will be recorded as updates to the subject's medical history.

In the SOC alone arm: Adverse event solicitation and recording will begin following the completion of all baseline assessments.

Clinical events related to the progression of COVID-19 will **not** be considered AEs.

Adverse events are summarized by subject incidence rates; therefore, in any tabulation, a subject contributes only once to the count for a given AE in both SOC and preferred term.

The number and percentage of patients with any TEAE, with any TEAE assessed by the Investigator as related to treatment, with any serious TEAE, and with any treatment-emergent serious AE (SAE) potentially related to treatment will be summarized by treatment group and overall.

All AEs occurring on-study will be listed in subject data listings.

By-subject listings also will be provided for the following: subject deaths, SAEs, and AEs leading to treatment/study discontinuation.

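### Protocol 9.7 takes between-arm differences for treatment-related events that SOC alone cannot score, while SAP 4.5.2 drops the differences that are valid

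*Protocol*

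**What the plan says.** Protocol 9.7 plans an overall TEAE summary by arm. Its rows include "any treatment-related TEAE, any serious TEAE, any treatment-related serious TEAE", then "TEAEs leading to study infusion discontinuation, treatment-related TEAEs leading to study infusion discontinuation", and finally TEAEs leading to death, in total and treatment-related. With the opening row for any TEAE, that makes eight. The section then says: "The difference in proportions between treatment groups in each of these categories will be calculated".

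Protocol 8.4.3 sets the causality rule: "The relationship of the Adverse Event to the study drug will be determined by the Principal Investigator". An event counts as related only if, among other conditions, "There is a distinct temporal relationship between the event onset and administration of the study drug".

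The control arm has no placebo. Under Protocol Section 3, subjects are randomised "to receive either favipiravir + standard of care (SOC) or SOC alone". Protocol 9.4 and SAP 2.1 analyse the safety population as treated. On route, the synopsis says: "Favipiravir tablets will be administered orally".

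SAP 4.5.2 keeps four summary rows: any TEAE, any related TEAE, any serious TEAE, and related serious events. The sentence ends "with any treatment-emergent serious AE (SAE) potentially related to treatment will be summarized by treatment group and overall". It mentions no difference between arms and puts events leading to discontinuation in a listing. SAP Section 5 names one departure from the protocol, the removal of hierarchical testing.

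**The concern.** A stated secondary objective (Protocol 4.2, item 4) is the safety of favipiravir added to SOC relative to SOC alone. That needs adverse event categories that both arms can score in the same way.

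Protocol 9.7 applies one instruction to all eight rows, whether or not SOC can contribute events. Where SOC is fixed at zero, the table would show a number labelled as a between-arm difference that is really a one-arm rate. A reader of the study report could take it for a controlled estimate of excess risk.

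The SAP does not resolve this by choosing the right rows. It leaves out every difference, so any TEAE and any serious TEAE lose the contrast the protocol promised. Because Section 5 is silent, it is unclear whether the omission was a decision or an oversight.

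**Working it through.** **Step 1. Classify the eight rows of Protocol 9.7 under Protocol 8.4.3.**

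| Row | Can SOC alone score it? |
|---|---|
| Any TEAE | Yes |
| Related TEAE | No |
| Serious TEAE | Yes |
| Related serious TEAE | No |
| TEAE leading to infusion discontinuation | Not as worded, in either arm; unclear if read as drug discontinuation |
| Related TEAE leading to infusion discontinuation | No |
| TEAE leading to death | Yes |
| Related TEAE leading to death | No |

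Four rows are structurally zero in SOC, one is undefined, and three are valid comparisons. As-treated assignment closes the remaining route: a SOC subject who took favipiravir would not be counted under SOC alone.

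**Step 2. Arm size.** The plan gives no figure for these rows, so the only plan number used is 25 per arm. It reproduces.
- HR = 4/11 = 0.364.
- Freedman events = (1.645 + 1.282)² × [(1 + HR)/(1 − HR)]² = 39.3.
- Exponential 15-day clearance probabilities are 1 − 2^(−15/4) = 0.926 and 1 − 2^(−15/11) = 0.611, mean 0.769.
- 39.3/0.769 = about 51 in total, against the planned 50.

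**Step 3. Behaviour of a related-event row.** Let p be the probability that a favipiravir subject has a related event. The documents give no value, so p is an assumption shown over a range. With SOC at 0/25:
- Expected difference = p − 0 = p.
- P(difference < 0) = 0.
- P(difference = 0) = (1 − p)^25.
- P(difference > 0) = 1 − (1 − p)^25.

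| p (assumed) | P(zero) | P(positive) | P(negative) |
|---|---|---|---|
| 1% | 78% | 22% | 0 |
| 5% | 28% | 72% | 0 |
| 10% | 7% | 93% | 0 |
| 20% | 0.4% | 99.6% | 0 |

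For contrast, suppose both arms could score the event at the same rate. A positive and a negative difference would then be equally likely: 36% each at 5%, 40% each at 10%, and 43% each at 20%.

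**Step 4. Compare the SAP.** Of the three valid rows, SAP 4.5.2 tabulates any TEAE and any serious TEAE by arm without a difference. Deaths are listed there, and SAP 4.3.2.7 gives a severity-adjusted relative risk for all-cause mortality with a 90% CI. The missing contrasts are therefore any TEAE and any serious TEAE.

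**Step 5. Precision of the missing contrasts.** The Wald 90% half-width at 25 per arm is 1.645 × √[2p(1 − p)/25]. At an assumed 20% in each arm it is 1.645 × √(0.32/25) = 0.186, about 19 points. At an assumed 50% it is 1.645 × √(0.50/25) = 0.233, about 23 points.

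**The case against.** The strongest reply is that the SAP governs the outputs. Protocol 9.1 leaves full analysis detail to the SAP, and SAP 4.5.2 plans no difference for any related or discontinuation row. The misleading numbers may never be produced. That stands as far as it goes, but the two documents then disagree without explanation, and the valid contrasts are lost with the invalid ones.

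Second, the related definition also requires that the subject's clinical state or other factors cannot explain the event. If investigators attribute correctly, the favipiravir rate does measure drug-caused harm. This is fair, but it supports reporting a one-arm rate, not a between-arm difference.

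Several stronger readings are tempting, and the documents do not support them:
- *The difference always counts against favipiravir.* It is zero whenever favipiravir has no such event, which is likely for rare rows such as related deaths.
- *The discontinuation rows are firmly zero in SOC.* The related one is. The all-cause one is not settled: the endpoint definition of time to clinical recovery counts SOC alone as a study treatment, and SAP 4.1 defines treatment completion for SOC and tabulates treatment discontinuation by arm. Read literally, the infusion rows are empty in both arms and favour neither.
- *The structural zero would yield a significant safety signal.* Protocol 9.7 specifies a difference, not a test, and SAP 3.3 confines formal testing to the primary and secondary efficacy endpoints.
- *The overall column misstates the related rate.* It is a correct pooled proportion, shown beside the by-arm figures. It is merely uninformative for an event that only one arm can score.
- *The SAP has no between-arm safety estimate.* Mortality has one.

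**Conclusion.** The point holds for the four treatment-related rows of Protocol 9.7. Under Protocol 8.4.3 their between-arm difference equals favipiravir's own rate and carries no information from SOC. This rests on the protocol's causality definition and as-treated analysis. The SAP refers to relatedness to treatment rather than to study drug, and neither document says how relatedness would be scored under SOC alone.

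The infusion wording is an error for an oral drug. Read as study-drug discontinuation, those rows still have no clear SOC counterpart. The SAP's omission of the differences for any TEAE and any serious TEAE is an undeclared departure from the protocol.

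The consequence is limited. Proof of concept rests on viral clearance (Protocol 9.1), and no stated decision turns on these rows. The correction is still worth making, because it bears directly on the secondary safety objective and uses data already collected.

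**What to change.** In Protocol 9.7 and SAP 4.5.2:
1. Report related TEAEs, and TEAEs leading to discontinuation of study drug (replacing the infusion wording), descriptively for the favipiravir arm, with that arm's denominator and no between-arm difference.
2. Give the risk difference with a 90% CI, the level used in SAP 3.3, for any TEAE, any serious TEAE and TEAE leading to death. Cross-refer to SAP 4.3.2.7 for all-cause mortality.
3. Record the change in SAP Section 5.

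The cost is a few table-shell and wording edits and two or three risk differences, with no new data. At about 25 per arm these estimates will be imprecise, and the report should say so.

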10 RECORDING AND COLLECTION OF DATA

10.1 Case Report Form

The Investigator or designee will record all data collected on the electronic Case Report Form (eCRF) provided for that purpose. The site will be suitably trained on the use of the eCRF and appropriate site personnel will be provided electronic signatures.

All site entries will be made in a secured web site and the Principal Investigator will review the record for completeness. Upon completion of the review, the PI will sign electronically in the signature page of the eCRF.

The Investigator or designee will make necessary eCRF corrections. The investigator must authorize the corrections to the entered data on eCRF.

Specific instructions on use of the EDC system and guidelines for data entry and correction will be provided to the sites.

10.2 Study Files and Subject Source Documents

Subject confidentiality is strictly held in trust by the participating investigators, research staff, the Sponsor and their designees. This confidentiality is extended to cover testing of biological samples in addition to the clinical information relating to subjects. Authorized representatives of the Sponsor may inspect all documents and records required to be maintained by the Investigator, including but not limited to, medical records (office, clinic or hospital) and pharmacy records for the subjects in this study. Any data, specimens, forms, reports, and other records that leave the site will be identified only by a subject identification number to maintain confidentiality.

The Investigator must maintain adequate and accurate records to enable the conduct of the study to be fully documented and the study data to be subsequently verified. These documents include Investigators' Study Files and original subject clinical source documents generated at the study site. The term "original" means the first recording of the data.

The Investigator will ensure the site master files are maintained, including the study protocol and its amendments, IRB and regulatory approvals with associated correspondence, informed consents, study drug records, staff curriculum vitae, all correspondence, and other appropriate documents.

Subject clinical source documents may include, but are not limited to, subject hospital/clinic records, physicians' and nurses' notes, appointment books, laboratory reports, ECGs, radiographs, and consultant letters. The Investigator must assure that all original source documents are available to support monitoring activities.

